### **6.3. Appendix 3: Supporting Study Information**

#### **6.3.1. Demographic**

Demographic parameters will be listed for the Safety populations.

#### **6.3.2. Baseline and Disease Characteristics**

Baseline characteristics (weight; height; and body mass index, calculated as weight [kg]/(height [m])) will be listed for the Safety.

#### **6.3.3. Protocol Deviations**

Protocol deviations will be defined in Protocol Deviation Requirement Specification, including importance classification. Participants with important protocol deviations will be listed for Safety population.

#### **6.3.4. Medical History**

Medical history in this study will be collected for participants who have a gap between the last visit of the lead-in study and Visit 1 of this extension study and only new medical history collected during the gap will be listed.

Abnormalities in participants' medical and surgical history will be coded using the Medical Dictionary for Regulatory Activities, version 23.0 or newer. Participants with abnormalities in medical and surgical histories from the lead-in study in each system organ class (SOC) and preferred term (PT) will be listed for the Safety population.

Migraine history, including diagnosis, duration of disorder, use of migraine prevention medication in the past, average number of migraine or headache days per month in the last 3 months, acute medications taken to treat migraine headaches, and advice on lifestyle alterations from the lead-in study will be listed for the Safety population.

#### **6.3.5. Prior/Concomitant medications**

*Prior medication* is defined as any medication taken before the date of the first dose of lead-in study treatment.

*Concomitant medication* for this study is defined as any medication taken on or after the date of the first dose of open-label study treatment.

Participants will be listed by Anatomical Therapeutic Chemical (ATC) 4 class and preferred term (PT) for both prior medications and concomitant medications in the Safety population.

Concomitant medications will be listed for the Safety Population.

If a participant took a specific medication multiple times or took multiple medications within a specific therapeutic class, that participant would be counted only once for the coded drug name or therapeutic class. Any prior and concomitant medications will be included in listings.

The medication data will be coded using the World Health Organization (WHO) Drug Global B3 version March 2019 or higher.

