3.1 Structure

This is a multicenter, open-label, 12-week, safety extension study conducted in China. Participants will be treated with atogepant 60 mg once daily.

The study will consist of a 12-week treatment period and a 4-week safety follow-up period.

After signing the informed consent, Chinese participants will directly rollover from Study 3101-303-002 (Phase 3 CM); hereafter referred to as the lead-in study. As such, participants will have Visit 7 from the lead-in study function as Visit 1 for this extension study. After Visit 1, study visits will occur every 4 weeks during the 12-week treatment period. A safety follow-up visit will occur 4 weeks after the last dose of atogepant.

Note, there may be participants who complete Visit 7 in the lead-in study before this extension study (3101-311-002) has been initiated. Those participants should complete Visit 7/ET and Visit 8/EOS Visit (including discontinuation of study intervention) per the lead-in study Schedule of Visits and Procedures.

Depending on the timing of the initiation of this extension study (3101-311-002) in relation to each participant's planned Visit 8 schedule in the lead-in study, Visit 1 for this extension study can be conducted on the same day as Visit 8/EOS Visit for the lead-in study, or soon thereafter.

- If this extension study is initiated prior to the participant's planned Visit 8 in the lead-in study, then Visit 8/EOS Visit in the lead-in study should be conducted on the same day as Visit 1 for this extension study (3101-311-002).
- If this extension study is not initiated prior to the participant's planned Visit 8 in the lead-in study (ie, there is a gap between Visit 8 of the lead-in study and Visit 1 of this extension study), then Visit 8/EOS Visit should be conducted as planned per the lead-in study Schedule of Visits and Procedures. When this extension study is initiated, the participant should return to the clinic as soon as possible, and Visit 1 should be conducted per [Table 1](#) Schedule of Visits and Procedures.

Participants will return to the clinic for safety assessments at 4, 8, and 12 weeks relative to Visit 1 (Day 1). A safety follow-up visit will occur 4 weeks after the last dose of atogepant 60 mg once daily. For details, please see [Table 1](#) Schedule of Visits and Procedures.

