4.5.2 Prohibited Medications/Treatments

The following medications are prohibited 30 days prior to Visit 1 (unless otherwise indicated) and throughout the study (see [Attachment 12.2](#)):

- Strong CYP3A4 inhibitors, including but not limited to: systemic (oral/IV) itraconazole, ketoconazole, erythromycin, clarithromycin, telithromycin, nefazodone, and HIV protease inhibitors
- Strong and moderate CYP3A4 inducers, including but not limited to: barbiturates (eg, phenobarbital and primidone), systemic (oral/IV) glucocorticoids, nevirapine, efavirenz, pioglitazone, carbamazepine, phenytoin, rifampin, rifabutin, and St. John's wort
- Strong OATP1B1 and OATP1B3 inhibitors (eg, gemfibrozil, cyclosporine)
- Drugs with narrow therapeutic margins with theoretical potential for CYP drug interactions (eg, warfarin)
- Medications with demonstrated efficacy for the prevention of migraine (eg, amitriptyline, topiramate, propranolol), excepting 1 medication with demonstrated efficacy for the prevention of migraine taken at a stable dose during lead-in study 3101-303-002, which may be continued if the participant is willing and able to do so (see Exclusion Criterion 1, Section [4.4](#)).
- CBD oil
- Therapeutic or cosmetic botulinum toxin injections (eg, Dysport®, Botox®, Xeomin®, Myobloc®, Jeuveau™) into areas of the head, face, or neck within 6 months prior to Visit 1 and throughout the study period
- Injectable monoclonal antibodies blocking the CGRP pathway (eg, Aimovig™, Emgality™, Ajovy®, Vygepti™) within 6 months prior to Visit 1 and through the study period.
- Herbal and traditional medicine is prohibited from the time the ICF is signed and for the duration of study participation.

The decision to administer a prohibited medication/treatment is done with the safety of the study participant as the primary consideration. When possible, the sponsor should be notified before the prohibited medication/treatment is administered.

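### Does SAP 6.3.5 lose medications taken only between the first lead-in dose and the first open-label dose?

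*SAP*

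**What the plan says.** SAP 6.3.5 defines two classes. A prior medication "is defined as any medication taken before the date of the first dose of lead-in study treatment". A concomitant medication "for this study is defined as any medication taken on or after the date of the first dose of open-label study treatment". The output commitment is: "Any prior and concomitant medications will be included in listings". SAP 6.4.9 imputes partial dates for the same two classes and adds no third.

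Protocol 3.1 allows for the case where "there is a gap between Visit 8 of the lead-in study and Visit 1 of this extension study". In that case, once the extension opens, "the participant should return to the clinic as soon as possible"; no maximum delay is given. SAP 6.3.4 deals with this gap for medical history, saying that "only new medical history collected during the gap will be listed". SAP 6.3.5 has no parallel sentence for medications.

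Protocol 4.5.2 sets look-back windows that end at Visit 1: "The following medications are prohibited 30 days prior to Visit 1 (unless otherwise indicated) and throughout the study". For some treatments, such as "Injectable monoclonal antibodies blocking the CGRP pathway", the window is 6 months.

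SAP section 3 expects about 3 participants, and the SAP version history records that summary tables were replaced by listings for that reason. SAP section 1 places the listing specifications in a separate document.

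**The concern.** The two definitions do not meet. One class closes at the first lead-in dose and the other opens at the first open-label dose. A course confined to the time between has no class, and so no express promise that it will be listed. A single injection in that interval always falls there, because it starts and stops on the same day.

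The interval is relevant to the plan's own rules. The 30-day and 6-month look-backs can fall wholly or partly inside it. A drug taken in a gap could also bear on how a Visit 1 laboratory value or an early adverse event is read. The contrast with SAP 6.3.4 makes it look like an oversight: a diagnosis made in the gap would be listed, while a drug course confined to the gap might not be. Since listings are now the main output, the wording of a listing commitment carries more weight than usual.

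**Working it through.** The plan gives no figure to reproduce. The check is one of logic, using the two definitions in SAP 6.3.5.

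**Step 1: complete dates.** Let L be the first lead-in dose and O the first open-label dose. A medication is prior if its start is before L, and concomitant if its stop is on or after O.

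| Start | Stop | Class |
|---|---|---|
| before L | before L | prior |
| before L | L to the day before O | prior |
| before L | on or after O | both |
| L to the day before O | L to the day before O | **neither** |
| L to the day before O | on or after O | concomitant |
| on or after O | on or after O | concomitant |

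One pattern of six is in neither class. This counts logical cases; it does not measure how many medications or participants are involved.

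**Step 2: partial dates.** Imputation moves records across the edges of the interval in both directions.

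- *Into the hole.* Take illustrative dates in one year: L = 10 March, O = 2 June. A drug truly started on 3 March is recorded only as March and stopped on 20 April. SAP 6.4.9.1 assigns the last day of the month when that month precedes the month of the first open-label dose, giving 31 March. Then 31 March is after L and 20 April is before O, so a truly prior drug has no class.
- *Out of the hole.* A gap medication's stop date lacks month and day, and its year is that of the last dose. SAP 6.4.9.2 assigns the last-dose date. That date is on or after O, so the drug counts as concomitant and is listed.

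The count of one in six therefore holds for complete dates only.

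**Step 3: who could be affected.** Protocol 3.1 gives three entry routes.

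| Route | Gap between studies |
|---|---|
| Lead-in Visit 7 serves as Visit 1 | 0 days |
| Visit 1 on the day of lead-in Visit 8 | 0 days |
| Visit 1 after lead-in Visit 8 | above 0 days, no maximum stated |

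On the first two routes the interval from L to O lies within the lead-in study's own visits. That the lead-in study reports these medications is an assumption, since its documents are not available. On the third route, the time after Visit 8 belongs to neither study. The documents do not say how many of the approximately 3 participants take it, so the range is 0 to 3.

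**Step 4: what depends on the listing.**

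- SAP section 4 defines the Safety and mITT populations by dosing and evaluable eDiary periods, and the Screened population by consent. Medication class plays no part.
- The efficacy endpoint comes from eDiary records (SAP 6.4.2.1). Acute medication use is also taken from the eDiary.
- No planned summary uses the prior or concomitant label. SAP 6.3.5 ends in listings.
- A prohibited drug taken within its look-back window breaches Protocol 4.5.2. SAP 6.3.3 lists it if the deviation is classed as important.
- For adjudicated ALT or AST elevations of at least 3 × ULN, SAP 5.4.4.1 lists confounding factors. Protocol 8.9 also screens ALT, AST and bilirubin at Visit 1.

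None of these results changes with the class given to a gap-only medication.

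**The case for a change.** The strongest case for a change is that the hole is in the text and is cheap to close. The same section defines both terms, so reading the listing sentence as covering all medications is generous. The sponsor recognised the gap and provided for it in medical history alone. The deviation route is incomplete: only important deviations are listed, and herbal and traditional medicine is barred only from consent, so a herbal course finished in the gap, if not otherwise prohibited, breaks no stated rule and would not appear there. One or two sentences would settle it.

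The textual point stands, and so does the incompleteness of the other routes. The inference that these medications will go unlisted does not. The listing specification is a separate document that was not available, and the SAP supports only the narrower statement that it does not expressly commit to listing them.

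Nor is it clear that a revised sentence would recover anything. Protocol 8.4.1.1 and 8.7 have sites update medications and ask about new ones since the last visit, which suggests that gap courses may be recorded. However, Protocol 10.6.1 asks for medications in use at enrollment, and the explicit gap instruction in Table 1, footnote b, covers medical history only. A listing cannot show what was not collected, and what was collected can be listed without any new definition.

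**Conclusion.** The definitions leave a real but inconsequential hole, and no change to the plan is needed. With complete dates, a medication started on or after the first lead-in dose and stopped before the first open-label dose has no class. Partial dates can move a record into or out of that interval. The practical reach is limited to participants with a gap between lead-in Visit 8 and Visit 1: 0 to 3 people, number not stated.

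No estimate, population, summary or safety conclusion turns on the missing class. With about 3 participants and a plan built on listings, the sensible default is to print every medication recorded in this study with its dates as recorded, whatever its label. SAP 5.1 already has partial dates listed as they appear on the eCRF.

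This rests on two assumptions that the documents do not settle: that medications used during the lead-in are reported in that study, and that the separate listing specification, or the analyst applying it, does not drop records merely because they fall between the two definitions.

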### 6.3.6. Adverse Events of Special Interest

Per the 3101-311-002 Protocol Section 6.1.2, selected non-serious and serious adverse events are of special interest and will require immediate reporting, recording, and follow-up. The following events will be closely monitored:

- Treatment-emergent suicidal ideations with intent, with or without a plan, (ie, Type 4 or 5 on the C-SSRS) or any suicidal behaviors.
- Treatment-emergent elevated ALT or AST lab value  $\geq 3 \times$  ULN.
- Potential Hy's law cases: elevated ALT or AST lab value that is  $\geq 3 \times$  ULN and an elevated total bilirubin lab value that is  $\geq 2 \times$  ULN and, at the same time, an alkaline phosphatase lab value that is  $< 2 \times$  ULN.

The display of above are described in the corresponding SAP Sections [5.4.4.1](#) and [5.4.4.4](#).

### 6.3.7. Potentially Clinically Significant Criteria for Safety Endpoints

Laboratory values in conventional unit, the potentially clinically significant criteria for clinical laboratory parameters, Hepatic laboratory abnormalities, vital signs and ECG parameters are provided in the following sections.

#### 6.3.7.1. Laboratory values in Conventional Unit

##### 6.3.7.1.1. *Background*

All laboratory parameters are reported in the International System (SI) units as standard practice. In addition, selected laboratory parameters (listed in [Table 6-1](#)) will be reported in conventional units to facilitate interpretation and reporting for the CSR and future labeling.

##### 6.3.7.1.2. *List of Parameters Reported in Conventional Unit*

The list of selected parameters required to be reported in conventional unit is provided in [Table 6-1](#).

**Table 6-1** List of Selected Parameters Reported in Conventional Unit

Number	Laboratory Parameter	Conventional Unit	Decimal Places
1	Alanine Aminotransferase (SGPT)	U/L	0
2	Albumin	g/dL	1
3	Alkaline Phosphatase	U/L	0
4	Aspartate Aminotransferase (SGOT)	U/L	0
5	Bilirubin, Direct (Conjugated)	mg/dL	1
6	Bilirubin, Indirect (Unconjugated)	mg/dL	1
7	Bilirubin, Total	mg/dL	1
8	Blood Urea Nitrogen	mg/dL	0
9	Calcium	mg/dL	1
10	Cholesterol, HDL	mg/dL	0
11	Cholesterol, LDL	mg/dL	0
12	Cholesterol, LDL direct and calculated (combined) (This lab parameter could be the same as #11)	mg/dL	0
13	Cholesterol, Total	mg/dL	0
14	Creatine Kinase	U/L	0
15	Creatinine	mg/dL	1
16	Glucose	mg/dL	0
17	Insulin	uIU/mL	1
19	Uric Acid	mg/dL	1
20	Hemoglobin	g/dL	1

#### 6.3.7.1.3. Analysis and Reporting Format in Conventional Units

- 1) For individual clinical study reports for the central nervous system (CNS) projects, the selected laboratory parameters (Table 6-1) will be listed in conventional units
- 2) Participant narratives generated by the statistical programming team will also include the values in conventional units for the selected lab parameters (Table 6-1). That will be accomplished by presenting the values in conventional units within the parentheses next to the values in SI units. An example is provided in Table 6-2 for lab parameter 'Bilirubin, Total', for which 'umol/L' is the SI unit and 'mg/dL' is the conventional unit.

Table 6-2 Presenting Laboratory Data Using SI and Conventional Units in Narratives

LABORATORY DATA						
Lab Test	Test Name	Normal Range		VISIT01	VISIT05	VISIT07
		Low	High	2012-07-03	2012-08-07	2012-09-04
...						
CHEMISTRY	Bilirubin, Total (umol/L (mg/dL))	0 (0)	18.81 (1.1)	6.84 (0.4)	5.13 (0.3)	5.13 (0.3)
...						

### 6.3.7.2. Potentially Clinically Significant Criteria for Clinical Laboratory Parameters

Table 6-3 Potentially Clinically Significant Criteria for Clinical Laboratory Parameters

Category	Parameter	SI Unit	PCS Criteria	
			PCS Low	PCS High
Chemistry	Albumin	g/L	< 0.8 × LLN	> 1.2 × ULN
	Alanine aminotransferase	U/L	—	≥ 3.0 × ULN
	Alkaline phosphatase	U/L	—	≥ 3.0 × ULN
	Aspartate aminotransferase	U/L	—	≥ 3.0 × ULN
	Bicarbonate	mmol/L	< 0.9 × LLN	> 1.1 × ULN
	Bilirubin, total	μmol/L	—	≥ 1.5 × ULN
	Blood urea nitrogen	mmol/L	—	≥ 1.5 × ULN
	Calcium	mmol/L	< 0.9 × LLN	> 1.1 × ULN
	Chloride	mmol/L	< 0.9 × LLN	> 1.1 × ULN
	Cholesterol, total	mmol/L	—	> 1.6 × ULN
	Creatinine	μmol/L	—	≥ 1.5 × ULN
	Creatine kinase	U/L	—	> 2.0 × ULN
	Estimated glomerular filtration rate	mL/min/1.73m 	< 60	—
	Glucose, nonfasting	mmol/L	< 0.8 × LLN	> 2.0 × ULN
	Lactate dehydrogenase (LDH)	U/L	—	≥ 3.0 × ULN
	Phosphorus	mmol/L	< 0.9 × LLN	> 1.1 × ULN
	Potassium	mmol/L	< 0.9 × LLN	> 1.1 × ULN
	Protein, total	g/L	< 0.9 × LLN	> 1.1 × ULN
Hematology	Sodium	mmol/L	< 0.9 × LLN	> 1.1 × ULN
	Uric acid	μmol/L	—	> 1.2 × ULN
	Basophils, absolute cell count	10  /L	—	> 2.0 × ULN
	Eosinophils, absolute cell count	10  /L	—	> 2.0 × ULN
	Hematocrit	Ratio	< 0.9 × LLN	> 1.1 × ULN
	Hemoglobin	g/L	< 0.9 × LLN	> 1.1 × ULN
	Lymphocytes, absolute cell count	10  /L	< 0.7 × LLN	> 1.3 × ULN
	Monocytes, absolute cell count	10  /L	< 0.5 × LLN	> 2.0 × ULN
	Neutrophils, absolute cell count	10  /L	< 0.7 × LLN	> 1.3 × ULN
Urinalysis	Platelet count	10  /L	< 0.5 × LLN	> 1.5 × ULN
	Red blood cell count	10  /L	< 0.9 × LLN	> 1.1 × ULN
	White blood cell count	10  /L	< 0.9 × LLN	> 1.5 × ULN
	pH	pH	< 0.9 × LLN	> 1.1 × ULN
	Glucose	mmol/L	—	At least 1+
	Protein	g/L	—	At least 1+
	Specific gravity	—	—	> 1.1 × ULN

LLN = lower limit of normal value; ULN = upper limit of normal value; normal value provided by laboratory.

SI = Le Système International d'Unités (International System of Units).

### 6.3.7.3. Criteria for Hepatic Laboratory Abnormalities

Table 6-4 Criteria for Hepatic Laboratory Abnormalities

Laboratory Parameter	Categories
ALT	$\geq 1 \times \text{ULN}$
	$\geq 1.5 \times \text{ULN}$
	$\geq 2 \times \text{ULN}$
	$\geq 3 \times \text{ULN}$
	$\geq 5 \times \text{ULN}$
	$\geq 10 \times \text{ULN}$
	$\geq 20 \times \text{ULN}$
AST	$\geq 1 \times \text{ULN}$
	$\geq 1.5 \times \text{ULN}$
	$\geq 2 \times \text{ULN}$
	$\geq 3 \times \text{ULN}$
	$\geq 5 \times \text{ULN}$
	$\geq 10 \times \text{ULN}$
	$\geq 20 \times \text{ULN}$
ALT or AST	$\geq 1 \times \text{ULN}$
	$\geq 1.5 \times \text{ULN}$
	$\geq 2 \times \text{ULN}$
	$\geq 3 \times \text{ULN}$
	$\geq 5 \times \text{ULN}$
	$\geq 10 \times \text{ULN}$
	$\geq 20 \times \text{ULN}$
Bilirubin Total	$\geq 1 \times \text{ULN}$
	$\geq 1.5 \times \text{ULN}$
	$\geq 2 \times \text{ULN}$
	$\geq 3 \times \text{ULN}$
	$\geq 5 \times \text{ULN}$
	$\geq 10 \times \text{ULN}$
	$\geq 20 \times \text{ULN}$
Alkaline Phosphatase	$\geq 1 \times \text{ULN}$
	$\geq 1.5 \times \text{ULN}$
	$\geq 2 \times \text{ULN}$
	$\geq 3 \times \text{ULN}$
	$\geq 5 \times \text{ULN}$
	$\geq 10 \times \text{ULN}$
	$\geq 20 \times \text{ULN}$
Concurrent Elevations 	ALT or AST $\geq 3 \times \text{ULN}$ and Bilirubin Total $\geq 1.5 \times \text{ULN}$
	ALT or AST $\geq 3 \times \text{ULN}$ and Bilirubin Total $\geq 2 \times \text{ULN}$
Potential Hy's Law 	ALT or AST $\geq 3 \times \text{ULN}$ and Bilirubin Total $\geq 2 \times \text{ULN}$ and ALP $< 2 \times \text{ULN}$

ALT = alanine aminotransferase; AST = aspartate aminotransferase; TBL = total bilirubin; ALP = alkaline phosphatase; ULN = upper limit of normal (value provided by the laboratory).

 Elevations are from the same day

#### 6.3.7.4. Potentially Clinically Significant Criteria for Vital Signs

Table 6-5 Potentially Clinically Significant Criteria for Vital Signs

Parameter	Flag	Criteria	
		Observed Value	Change from Baseline
Systolic blood pressure, mm Hg	High	$\geq 180$	Increase of $\geq 20$
	Low	$\leq 90$	Decrease of $\geq 20$
Diastolic blood pressure, mm Hg	High	$\geq 105$	Increase of $\geq 15$
	Low	$\leq 50$	Decrease of $\geq 15$
Pulse rate, bpm	High	$\geq 120$	Increase of $\geq 15$
	Low	$\leq 50$	Decrease of $\geq 15$
Weight, kg	High	—	Increase of $\geq 7\%$
	Low	—	Decrease of $\geq 7\%$
Orthostatic SBP change, mm Hg	Low	$\leq -20$	—
Orthostatic DBP change, mm Hg	Low	$\leq -15$	—
Orthostatic Pulse rate change, bpm	High	$\geq 25$	—

SBP = Systolic blood pressure, DBP = Diastolic blood pressure, bpm = beats per minute.

#### 6.3.7.5. Potentially Clinically Significant Criteria for ECG parameters

Table 6-6 Potentially Clinically Significant Criteria for ECG parameters

Parameter	Unit	Criterion
QRS interval	msec	$\geq 150$
PR interval	msec	$\geq 250$
QTc (QTcB or QTcF) interval	msec	$> 500$
QTc (QTcB or QTcF) interval	msec	Increase from baseline $> 60$

QTc = QT interval corrected for heart rate.

QTcB = QT interval corrected for heart rate using the Bazett formula.

QTcF = QT interval corrected for heart rate using the Fridericia formula.

### 6.4. Data handling convention

Day 1 is defined as day for the date of the first dose of open-label study intervention. There is no Day 0 or Week 0. Treatment day is relative to the date of the first dose of open-label study intervention.

#### 6.4.1. Analysis Window

The analysis visit windows for monthly efficacy and health outcome (except for MSQ) endpoints based on daily eDiary data are defined as follows:

**Table 6-7 Efficacy and Health Outcome Analysis Visit Definitions for eDiary Data (Monthly)**

Analysis Phase	Analysis Visit (Derived)	eDiary Window
Lead-in Study	Baseline	Baseline from lead-in study
Open-label Treatment Period	Weeks 1 – 4	Treatment Day [1, 28]
	Weeks 5 – 8	Treatment Day [29, 56]
	Weeks 9 – 12	Treatment Day [57, 84]

The analysis visit windows for MSQ v2.1 are defined as follows:

